7.8. Temperature

No eating, drinking or smoking is allowed for 15 minutes prior to the measurement.

"Each part of the body has a unique temperature based on perfusion, hemodynamic circumstances, and thermal conditions" and because institutional standards for measurement of temperature may vary, this protocol will not restrict the accepted routes of temperature measurement. The route selected for each patient should be used consistently.

Investigators are therefore recommended "to evaluate temperature sites available and select the temperature measurement site depending on the patient's age and level of physiologic stability". ¹⁴ Furthermore, "an optimal thermometer should provide ease of application within a brief period, accurate temperature measurement, safety, tolerability by the patient, and no potential risks". ¹⁵

7.9. Blood Volume

The total PK blood sampling volume for individual subjects in this study is approximately 4.5 mL. If the actual PK sample collection times differ from the nominal times relative to dosing, the number of samples collected must remain the same. Additional blood samples may be taken for safety assessments at times specified by Pfizer, provided the total volume taken during the study does not exceed 550 mL during any period of 30 consecutive days.

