1.3.1. Dose Selection Rationale

Rationale for dose selection is based on:

- The safety and tolerability of 0.8 mg/kg and 1.6 mg/kg IV doses of pantoprazole sodium in children aged 1 to 2 years (3001K1-117) and 2 to 16 years respectively (3001K1-110).
- The efficacy, safety, and tolerability of 0.3 mg/kg to 1.2 mg/kg oral doses of pantoprazole sodium in children aged 1 to 5 years of age (3001B3-328).
- The efficacy of 20 mg and 40 mg oral doses of pantoprazole sodium in children aged 5 to 11 years of age (3001A1-322).
- The efficacy, safety, and tolerability of 20 mg and 40 mg oral doses of pantoprazole sodium in children aged 12 to 16 years of age (3001A1-326 and 3001A3-337).
- The exposures were approximately similar following IV and oral administrations, as the absolute bioavailability of pantoprazole is about 77%.
- According to population PK analysis across the age groups, the body weight was the most influencing covariate to clearance of pantoprazole in pediatric patients. FDA recommended that pediatric doses be based on body weight as well as age to match the adult exposure more closely. The proposed 10 mg dose for pediatric subjects aged 1 to <2 years (body weight 8 to <15 kg), 20 mg dose for 2 to 11 years (body weight >15 to <40 kg), and 40 mg dose for 12 to 16 years old (body weight ≥40 kg) are based on body weight and age of the patients in this study.
- Based on modeling and simulation analysis, the predicted systemic exposures (C_{max} and AUC) in patients aged 1 to < 2 years, 2 to 11 years, and 12 to 16 years at the respective doses of 10, 20 and 40 mg were similar to the exposures seen in adults.

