4.1. Inclusion Criteria

Subject eligibility should be reviewed and documented by an appropriately qualified member of the investigator's study team before subjects are included in the study.

Subjects must meet all of the following inclusion criteria to be eligible for enrollment into the study:

1. Evidence of a personally signed and dated informed consent document indicating that the parent/legal guardian has been informed of all pertinent aspects of the study.

- 2. Evidence of a personally signed and dated assent, indicating that the subject understands the nature of all pertinent aspects of the study, and is willing to participate in the study activities, if applicable, as consistent with the subject's age and ability to provide assent.
- 3. The subject (to degree appropriate for age) and parent or legal guardian are able to understand and comply with protocol requirements, instructions and protocol-stated restrictions and are likely to complete the study as planned.
- 4. Subjects aged 1 to 16 years who in the judgment of the investigator are candidates for gastric acid suppression therapy (ie, those with a presumptive diagnosis of GERD, a clinical diagnosis of suspected GERD, symptomatic GERD, or endoscopically proven GERD) and whom the investigator judges would need to receive IV PPI therapy for at least 4 days. See Section 7.1.
- 5. Physical examination and clinical laboratory evaluations within normal limits unless the investigator documents that the deviations are not clinically significant or are directly related to the reason for gastric acid suppression therapy or to the subject's underlying disease process.
- 6. Body weight >5th percentile for subject's age.
- 7. Y-site or dedicated IV line for administration of pantoprazole sodium.
- 8. Expected survival for at least 30 days.
- 9. The subject (to degree appropriate for age) and parent or legal guardian are willing and able to comply with scheduled visits, treatment plan, laboratory tests, and other study procedures.
- 10. Fertile male subjects and female subjects of childbearing potential and at risk for pregnancy must agree to use a highly effective method of contraception throughout the study and for at least 28 days after the last dose of assigned treatment.
 - a. If subject is a female of childbearing potential, she must agree to use adequate contraception and must have a negative serum pregnancy test within 24 hours prior to administration of investigational product.

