5.4. Administration

The pantoprazole sodium dose is fixed according to subject weight. See the Investigational Product Dosing Table below. The maximum dose per 24 hour period for a subject who weighs at least 40 kg will not exceed 40 mg, irrespective of weight or age. Pantoprazole sodium will be administered intravenously through a Y-site or dedicated line (if Y-site is used, IV line must be flushed before and after dose administration) once daily for 4 to 7 days, approximately every 24 hours, preferably in the morning. The IP Manual will be provided to the investigator site and include pantoprazole sodium administration instructions.

Investigational Product Dosing

IV Dose of Pantoprazole Sodium			
Subject Weight	Total Daily Dose		
Less than 15 kg	10 mg		
At least 15 kg to less than 40 kg	20 mg		
At least 40 kg	40 mg		

Pantoprazole sodium IV for Injection should be inspected visually for particulate matter and discoloration prior to and during administration whenever solution and container permit. When administered via a Y-site, immediately stop use if precipitation or discoloration occurs.

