6.1. Screening

Subjects will be screened on Day 0 or on Day 1 prior to investigational product administration to confirm that they meet the subject selection criteria for the study. The investigator (or an appropriate delegate at the investigator site) will obtain informed consent and assent (depending on subject age and ability to provide assent) from each subject/parent/legal guardian in accordance with section Subject Information and Consent. The following procedures will be obtained:

- Obtain written parent/legal guardian informed consent, assent as appropriate.
- Review Inclusion/Exclusion criteria.
- Complete medical history, including documentation of diagnosis of GERD (Section 7.1), all prescription or nonprescription drugs, vitamins, and dietary supplements taken prior to screening procedures.
- Obtain history of drug, alcohol and tobacco use.
- Conduct physical examination, including height and weight.

- Obtain vital signs (blood pressure, pulse rate, and temperature). If a pulse rate abnormality is detected, electrocardiogram (ECG) or rhythm strip should be obtained to document this.
- Collect blood and urine specimens for the following:
 - Safety laboratory tests (to minimize the amount of blood collected, laboratory studies performed within 1 week before investigational administration may serve as screening safety laboratory values provided the information specified in the protocol is obtained). See Section 7.5.
 - Pregnancy test for female subjects of childbearing potential.
- Assess symptoms/adverse events.
- Review prior or concomitant medications.

Laboratory results for standard care may serve as study entry labs (eg, safety laboratory tests and vital signs), provided they are collected within the protocol-specified timeframe.

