7.2. Pharmacokinetics

Blood samples (0.5 mL) for pharmacokinetic analysis of pantoprazole will be collected at times specified below. Pharmacokinetic blood samples (0.5 mL at each time point listed below) can be collected either by direct venipuncture or from an intravenous catheter. The samples must not be collected from a catheter that is connected to the study drug infusion line. The samples must be collected at a different access site that is not downstream from the site of drug administration. Additional details are found in the laboratory manual.

- Day 1: Venous blood samples (0.5 mL) will be collected to measure plasma concentrations of pantoprazole at 0.25 (the 0.25 hour sample is to be taken at the end of the 15-minute infusion), 1 to 2, 3 to 4, and 5 to 6 hours after the start of the infusion.
- Day 2: Venous blood samples (0.5 mL) will be immediately collected predose and at 0.25 (the 0.25 hour sample is to be taken at the end of the 15-minute infusion), 1 to 2, 3 to 4, and 5 to 6 hours after the start of the infusion.

Total blood sampling volume for PK analysis is approximately 4.5 mL for an individual subject.

If the actual PK sample collection times differ from the nominal times relative to dosing, the number of samples collected must remain the same. All efforts will be made to obtain the pharmacokinetic samples within the specified windows relative to dosing. However, samples obtained within \pm 15 minutes of the nominal time from dosing (ie, for the 1 to 2, 3 to 4, and 5 to 6 hour post-dose samples) will not be captured as a protocol deviation, as long as the exact time of the sample collection is noted on the source document and data collection tool (eg, CRF/DCT). The 0.25 hour (the 0.25 hour sample is to be taken at the end of the 15-minute infusion) sample must be taken at the exact nominal time relative to dosing.

Samples will be collected, processed, stored, and shipped according to the instructions provided by the sponsor to the investigator site under separate cover prior to study start.

As part of evaluation of the investigational product, samples may be used for evaluation of the bioanalytical method. These data will be used for internal exploratory purposes and will not be included in the clinical report. Samples collected for this purpose will be retained in accordance to local regulations and if not used within this timeframe, will be destroyed.

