7.5. Safety Laboratory

The following safety laboratory tests below will be performed at times defined in the Treatment Period section of this protocol. Additional laboratory results may be reported on these samples as a result of the method of analysis or the type of analyzer used by the clinical laboratory; or as derived from calculated values. These additional tests would not require additional collection of blood. Unscheduled clinical labs may be obtained at any time during the study to assess any perceived safety concerns (Table 1). To minimize the amount of blood collected, routine laboratory studies planned within 48 hours after the last dose of investigational product may be used as the final study evaluation safety laboratory values, provided the information specified in the protocol is obtained.

Table 1. Safety Labs

Hematology	Chemistry	Urinalysis	Other
Hemoglobin	Sodium	рН	Serum gastrin level
Hematocrit	Potassium	Specific gravity	(fasting if possible)
Red blood cell	Chloride	Protein/albumin	Serum or urine pregnancy test ^a
count with	Bicarbonate or CO2	Glucose/sugar	
indices (MCV,	Glucose	Ketones/acetone	
MCH, and	Bun or Urea	Blood/ hemoglobin	
MCHC)	Creatinine	Nitrites	
White blood cell	Uric acid	Leukocyte esterase	
count with	Magnesium	Bilirubin	
differential	Total bilirubin		
Platelet count	Total protein		
	Serum albumin		
	Aspartate aminotransferase		
	(AST)		
	Alanine aminotransferase		
	(ALT)		
	Creatine kinase (CK)		
	Alkaline phosphatase (ALP)		

a. For female subjects of childbearing potential, a serum pregnancy test, with sensitivity of at least 25 mIU/mL, will be performed at screening, within 24 hours before investigational product administration. On the day after the last dose, a serum or urine pregnancy test, with sensitivity of at least 25 mIU/mL will be performed. Pregnancy tests may also be repeated as per request of IRB/IECs or if required by local regulations.

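### The flat 550 mL per 30 days blood limit in Protocol Section 7.9 is not scaled to weight and cannot protect a child of 8 to 15 kg

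*Protocol*

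**What the plan says.** Protocol Section 7.9 gives the planned PK volume and then allows additional samples for safety assessments, at times the sponsor specifies, "provided the total volume taken during the study does not exceed 550 mL during any period of 30 consecutive days". It sets no condition on age or weight and gives no mL/kg figure.

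The study enrolls children from 1 to 16 years. Section 1.3.1 describes the youngest group this way: "The proposed 10 mg dose for pediatric subjects aged 1 to <2 years (body weight 8 to <15 kg". Entry has no minimum weight in kg. Section 4.1 asks only for "Body weight >5th percentile for subject's age", and the lowest band of the dosing table in Section 5.4 is "Less than 15 kg".

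On planned blood, Section 7.2 states: "Total blood sampling volume for PK analysis is approximately 4.5 mL for an individual subject". Safety laboratory tests are scheduled at screening and on the day after the last dose, but their volume in mL is not given. Section 7.5 adds: "Unscheduled clinical labs may be obtained at any time during the study to assess any perceived safety concerns".

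The protocol does aim to spare blood. Section 6.1 says "to minimize the amount of blood collected, laboratory studies performed within 1 week before investigational administration may serve as screening safety laboratory values", and the Schedule of Activities, Section 6.3 and Section 7.5 allow similar re-use of routine results after the last dose. None of these provisions carries a number. The SAP sets no blood limit.

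**The concern.** A volume ceiling matters mainly for draws that were not planned, and the protocol foresees such draws. Section 7.9 lets the sponsor specify additional samples, and Section 7.5 allows unscheduled tests whenever there is a safety concern. The work-up for possible drug-induced liver injury in Section 8.6.2 calls for repeat transaminases, bilirubin fractions, gamma-glutamyl transferase, PT/INR and other tests, with hepatitis serology if warranted.

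For a toddler, a limit of 550 mL would not be reached until roughly half to all of the circulating volume had been taken. It therefore gives a site no usable stopping point, and a draw that was excessive for the child would not count as a deviation from Section 7.9. Because the safety-panel volume is not stated, a site or ethics committee cannot work out a child's total study volume from the protocol and compare it with any limit.

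**Working it through.** **Inputs from the protocol.** Limit 550 mL per 30 days (Section 7.9). Cohort 1 weight 8 to <15 kg (Section 1.3.1). The 40 kg boundary of the top dosing band (Section 5.4), used for comparison. PK samples of 0.5 mL, four on Day 1 and five on Day 2 (Section 7.2). Two scheduled safety panels (Schedule of Activities).

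**Assumptions not in the documents.** Circulating volume 65 to 85 mL/kg. Blood per safety panel 3 to 10 mL, with 30 mL as an extreme case.

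**Step 1: reproduce the stated PK volume.** (4 + 5) × 0.5 mL = 4.5 mL, which agrees with Sections 7.2 and 7.9. Per kg this is 4.5/8 = 0.56 mL/kg at 8 kg and 4.5/15 = 0.30 mL/kg at 15 kg.

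**Step 2: express the limit per kg and as a share of blood volume.** Limit per kg = 550/weight. Share = limit per kg divided by 85 (low end) and by 65 (high end).

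| Weight | 550/weight | Share of circulating volume |
|---|---|---|
| 8 kg | 68.8 mL/kg | 81-106% |
| 10 kg | 55.0 mL/kg | 65-85% |
| 15 kg | 36.7 mL/kg | 43-56% |
| 40 kg | 13.8 mL/kg | 16-21% |

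The 8 kg bound comes from the dose rationale and is not an entry criterion. An eligible child below 8 kg would have a still higher figure per kg.

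**Step 3: find when the limit would bind.** After PK, 550 − 4.5 = 545.5 mL remains. Spread over the two scheduled panels, that is 545.5/2 = 272.75, or about 273 mL per panel.

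**Step 4: compare with planned use.** Planned total = 4.5 + 2 × panel volume.

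- At 3 mL per panel the total is 10.5 mL, and at 10 mL per panel it is 24.5 mL.
- At 8 kg this is 10.5/8 = 1.31 to 24.5/8 = 3.06 mL/kg, or 1.5% (1.31/85) to 4.7% (3.06/65) of blood volume.
- At 15 kg it is 0.70 to 1.63 mL/kg, or 0.8% to 2.5%.
- The limit is 550/24.5 = 22 to 550/10.5 = 52 times the planned total.
- With 30 mL per panel the total is 64.5 mL, still only 64.5/550 = 11.7% of the limit.

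**Step 5: an illustrative unplanned case.** If 100 mL were drawn from an 8 kg child, that would be 12.5 mL/kg. This is 12.5/85 = 15% to 12.5/65 = 19% of blood volume, yet only 100/550 = 18% of the limit.

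**The case against.** The strongest reply is that nobody would come near 550 mL, and that other controls protect the child:

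- The allowance in Section 7.9 is confined to safety samples at times the sponsor specifies.
- PK volume is effectively fixed, because the number of samples may not change if collection times shift.
- Either safety panel may be replaced by routine results, so the added volume could be close to zero.
- Section 7 obliges the investigator to protect the subject's wellbeing, and Section 12.1 requires prospective ethics approval.
- The laboratory manual cited in Section 7.2 is not available here and may set a tighter limit.
- Unscheduled tests in a hospitalized child serve that child's care, and a study ceiling should not obstruct them.

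Much of this is right, and it limits how serious the point is. Planned exposure is low, the protections are real, and 273 mL per panel describes nothing anyone intends to do. It is also fair that the limit's failure to bind is a practical judgment, because neither panel volume nor circulating volume is documented.

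It does not rescue the number. Specifying times controls when blood is drawn and not how much. The other protections carry no figure, and the one figure that is given permits far more than they would be expected to allow. Section 7.9 does not defer to the laboratory manual; if a tighter limit stands there, Section 7.9 should state it. The concern about clinical care is met by confining the ceiling to study samples.

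**Conclusion.** The concern holds. Section 7.9 states a safety threshold that is wrong for the population. It is one fixed volume for ages 1 to 16 years, equal to about 37 to 69 mL/kg across the Cohort 1 weight range. Those per-kg figures follow from the protocol's numbers alone.

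The statement that this is roughly 43-106% of a Cohort 1 child's blood depends on the assumed 65 to 85 mL/kg. No value in that range makes the limit meaningful for a toddler. The gap between limit and planned use depends on the assumed panel volumes, but the planned total stays below about 12% of the limit even at 30 mL per panel.

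This should be fixed. It is a fault in the written safeguard only: estimation of CL and Vd, the sample size and the safety summaries are unaffected, and nothing suggests that excessive sampling is planned.

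**What to change.** Delete the 550 mL figure from Section 7.9 and make two changes.

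1. Set a ceiling in mL per kg body weight per 30 days, covering PK, scheduled safety and unscheduled study samples together. The sponsor's pediatric clinicians should choose the value, which cannot be derived from the documents. Say explicitly that tests needed for the child's own clinical care are not restricted by it.
2. State the blood volume of each safety panel and the expected study total (PK plus both panels) for the smallest eligible child, and confirm that this total fits under the ceiling.

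The text change is short. The sponsor must establish the panel volumes, and the amendment needs IRB/IEC approval under Section 12.1. If the panels come close to the new ceiling in the smallest children, sites may need low-volume tubes or more re-use of routine laboratory results, which the protocol already permits.

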8. ADVERSE EVENT REPORTING

8.1. Adverse Events

All observed or volunteered AEs regardless of treatment group or suspected causal relationship to the investigational product(s) will be reported as described in the following sections.

For all AEs, the investigator must pursue and obtain information adequate both to determine the outcome of the AE and to assess whether it meets the criteria for classification as a serious adverse event (SAE) requiring immediate notification to Pfizer or its designated representative. For all AEs, sufficient information should be obtained by the investigator to determine the causality of the AE. The investigator is required to assess causality. Follow-up by the investigator may be required until the event or its sequelae resolve or stabilize at a level acceptable to the investigator, and Pfizer concurs with that assessment.

As part of ongoing safety reviews conducted by the Sponsor, any non-serious adverse event that is determined by the Sponsor to be serious will be reported by the Sponsor as an SAE. To assist in the determination of case seriousness further information may be requested from the investigator to provide clarity and understanding of the event in the context of the clinical study.

8.2. Reporting Period

For SAEs, the active reporting period to Pfizer or its designated representative begins from the time that the subject provides informed consent, which is obtained prior to the subject's participation in the study, ie, prior to undergoing any study-related procedure and/or receiving investigational product, through and including 28 calendar days after the last administration of the investigational product. Serious adverse events occurring to a subject after the active reporting period has ended should be reported to the Sponsor if the investigator becomes aware of them; at a minimum, all serious adverse events that the investigator believes have at least a reasonable possibility of being related to investigational product are to be reported to the Sponsor.

AEs (serious and non-serious) should be recorded on the case report form (CRF) from the time the subject has taken at least one dose of investigational product through the subject's last visit.

8.3. Definition of an Adverse Event

An AE is any untoward medical occurrence in a clinical investigation subject administered a product or medical device; the event need not necessarily have a causal relationship with the treatment or usage. Examples of AEs include but are not limited to:

- Abnormal test findings;
- Clinically significant symptoms and signs;
- Changes in physical examination findings;
- Hypersensitivity;
- Progression/worsening of underlying disease;
- Drug abuse;
- Drug dependency.

Additionally, they may include the signs or symptoms resulting from:

- Drug overdose;
- Drug withdrawal;
- Drug misuse;
- Drug interactions;
- Extravasation;
- Exposure during pregnancy (EDP);
- Exposure via breastfeeding;
- Medication error;
- Occupational exposure.

8.4. Medication Errors

Medication errors may result, in this study, from the administration or consumption of the wrong product, by the wrong subject, at the wrong time, or at the wrong dosage strength. Such medication errors occurring to a study participant are to be captured on the medication error CRF which is a specific version of the AE page and on the SAE form when appropriate. In the event of medication dosing error, the sponsor should be notified immediately.

Medication errors are reportable irrespective of the presence of an associated AE/SAE, including:

- Medication errors involving subject exposure to the investigational product;
- Potential medication errors or uses outside of what is foreseen in the protocol that do or do not involve the participating subject.

Whether or not the medication error is accompanied by an AE, as determined by the investigator, the medication error is captured on the medication error version of the AE page and, if applicable, any associated AE(s) are captured on an AE CRF page.

